Page 1 of 62

Protocol Number: 20130193 Date: 12 October 2022

Summary Table of Study Protocol

Title	A Postmarketing Prospective Cohort Study of Melanoma Patients Treated With IMLYGIC® (Talimogene Laherparepvec) in Clinical Practice to Characterize the Risk of Herpetic Infection Among Patients, Close Contacts, and Health Care Providers; and Long-term Safety in Treated Patients		
Protocol version identifier	20130193, Superseding Amendment 5		
Date of protocol version	Original: 18 April 2016 Amendment 1: 28 July 2016 Amendment 2: 12 April 2017 Amendment 3: 03 September 2020 Amendment 4: 26 August 2021 Amendment 5: 25 August 2022		
	Superseding Amendment 5: 12 October 2022		
European Union postauthorization study register number	EUPAS15128		
Active substance	Talimogene laherparepvec		
Medicinal product	IMLYGIC®		
Product reference	To be determined		
Procedure number	EMEA/H/C/002771		
Research question and objectives	The primary objective is to estimate the incidence rate of herpetic infection with detection of talimogene laherparepvec DNA among patients enrolled in Study 20130193 for up to 5 years after the first IMLYGIC dose		
Countries of study	Inclusion of specific countries will depend on postmarket use of product, local feasibility, and local regulatory requirements.		
Author	Center for Observational Research PPD PPD Center for Observational Research PPD Center for Observational Research PPD		

Protocol Number: 20130193 Date: 12 October 2022

Marketing Authorization Holder

Marketing authorization holder	Amgen Inc. [name] United States [name]		
Marketing authorization holder contact	PPD		

This protocol was developed, reviewed, and approved in accordance with Amgen's standard operating procedures.

Confidentiality Notice

This document contains confidential information of Amgen Inc.

This document must not be disclosed to anyone other than the site study staff and members of the Institutional Review Board/Independent Ethics Committee/Institutional Scientific Review Board or equivalent, as applicable.

The information in this document cannot be used for any purpose other than the evaluation or conduct of the research without the prior written consent of Amgen Inc.

If you have questions regarding how this document may be used or shared, call the Amgen Medical Information number: United States sites, [name]; for all other countries, [name].

Page 2 of 62

Amgen Proprietary - Confidential

Product: IMLYGIC®

Protocol Number: 20130193
Date: 12 October 2022
Page 3 of 62

Investigator's Agreement

I have read the attached protocol entitled "A Postmarketing Prospective Cohort Study of Melanoma Patients Treated With IMLYGIC® (Talimogene Laherparepvec) in Clinical Practice to Characterize the Risk of Herpetic Infection Among Patients, Close Contacts, and Health Care Providers; and Long-term Safety in Treated Patients", dated 12 October 2022, and agree to abide by all provisions set forth therein.

I agree to ensure that the confidential information contained in this document will not be used for any purpose other than the evaluation or conduct of the clinical investigation without the prior written consent of Amgen Inc.

Signature	
Name of Investigator	Date (DD Month YYYY)
Title:	
Name of Hospital/Site:	
Address/City/State/Country:	
Phone Number:	
Email:	

Protocol Number: 20130193 Date: 12 October 2022

[figure not shown]
Page 4 of 62

Study Design Schema

Follow-up

- observation during and after IMLYGIC® treatment
- during IMLYGIC treatment, study assessments at clinic visits for IMLYGIC treatment
- after discontinuation of IMLYGIC, study assessments every 3 months (± 30 days) via phone or routine clinic visits if they fall within the 30-day window

Collection of data from the following:

^a Median duration of IMLYGIC treatment was approximately 6 months in the clinical trial setting but may differ in clinical practice.

Protocol Number: 20130193

Date: 12 October 2022 Page 5 of 62

Table 1. Schedule of Assessments

	Screening ^a	Baseline	Assessments (approximately every 2 weeks) during IMLYGIC® treatmentb	Assessments (every 3 months ± 30 days) after discontinuation of IMLYGIC ^c
General assessments and medical history				
Written informed consent	х			
Review of eligibility criteria	х			
Patient demographics ^d		x		
Patient characteristics ^e		х		
Medical and surgical history ^f		х		
History of herpetic infection ^g		Х		
Signs and symptoms of herpetic infection ^h			х	х
Results of local laboratory testing of suspicious herpetic lesions for HSV-1, per standard of care	•		At any time –	•
Treatment received				
IMLYGIC ⁱ		X	x	
Other anticancer treatment ^j		X	x	х
Antiherpetic therapy ^k		X	x	х
Assessments of Safety and Survival				
Review of adverse events and serious adverse events during IMLYGIC treatment ^{l, m}		Х	х	
Review of IMLYGIC-related adverse events and serious adverse events that occur after discontinuation of IMLYGIC ⁿ				Х
Review of product complaints ^o		х	x	
Review of other safety findings ^p		х	х	
Survival assessment ^q			x	х

Page 1 of 2

Footnotes are defined on the next page of this table

Protocol Number: 20130193
Date: 12 October 2022
Page 6 of 62

Table 1. Schedule of Assessments

	Screening ^a	Baseline	Assessments (approximately every 2 weeks) during IMLYGIC® treatment ^b	Assessments (every 3 months ± 30 days) after discontinuation of IMLYGIC ^c		
Results from analysis of samples for talimogene lahe	Results from analysis of samples for talimogene laherparepvec DNA					
Patient ^r	◆ At any time →					
Close contact ^r	← At any time ←					
Health care provider ^r	◆ At any time →					

Page 2 of 2

HSV-1 = herpes simplex virus type 1, HCP = Health care provider, qPCR = quantitative polymerase chain reaction.

- ^a The study site will maintain a screening tally of patients receiving IMLYGIC that includes nonidentifying information about sex, age, **race**, **ethnicity**, and disease stage.
- ^b During IMLYGIC treatment, the study assessments are to be completed at the clinic visits for IMLYGIC treatment.
- ^c After discontinuation of IMLYGIC until the end of follow-up, the study assessments are to be completed every 3 months (± 30 days) via phone or routine clinic visits if they fall within the 30-day window.
- ^d Review the following patient demographics: age, sex, race, and ethnicity.
- e Review the following patient characteristics: Eastern Cooperative Oncology Group (ECOG) performance status and disease stage.
- ^f Review medical and surgical history:
 - surgical therapy
 - radiotherapy
 - local or regional therapy
 - systemic therapy
 - participation in clinical trials
- ⁹ Patient reports the following information on herpetic infections: type of infection, frequency, and testing; type of treatment.
- h Patient reports presence or absence of signs and symptoms of suspected herpetic infection since the time of last observation.
 - Patient's response ("yes" or "no") to the following question will be recorded: "Have you had any signs or symptoms of herpetic infection since your last visit?"
 - Examples of signs and symptoms include **but not limited to**: pain, burning, or tingling in a blister around the mouth or genitals, fingers, ears, **or any part of the body close to or far from the injection site**; eye pain, light sensitivity, discharge from the eyes, or blurry vision; weakness in arms or legs; extreme drowsiness; mental confusion.
 - If a patient answers "yes", then the following information about the infection will be collected: signs and symptoms, dates, reporting and testing for virus identification, and antiherpetic treatment received.
- Record the following information about IMLYGIC received: dates, dose concentration, injection volume.
- ¹ Record dates and types of other anticancer therapy received (see "f" for the list of therapies).
- ^k Record the following information about antiherpetic therapy received: dates, type (eg, acyclovir, valacyclovir, famciclovir, docosanol), administration route (oral, intravenous, topical).

Protocol Number: 20130193
Date: 12 October 2022
Page 7 of 62

Adverse events and serious adverse events that occur after the patient has signed the informed consent form (ICF) through 30 days after the last dose of IMLYGIC will be recorded in the electronic case report form (eCRF). Adverse events should be assessed on an ongoing basis.

- ^m Safety events which are considered serious must be submitted as individual case safety reports to Amgen via the applicable Amgen Safety Reporting Form (paper or electronic form) within 1 business day of Investigator's awareness.
- ⁿ Adverse events and serious adverse events that occur more than 30 days after the last dose of IMLYGIC and deemed by the Investigator to be related to treatment with IMLYGIC. **Any fatal outcome during long term follow up should be reported as a serious adverse event.**
- ^o Product complaints that occur after the patient has signed the ICF through 30 days after the last dose of IMLYGIC.
- P Other safety findings include, for example, medication errors, exposure to IMLYGIC during pregnancy and breastfeeding, accidental exposure, that occur after the patient has signed the ICF through 30 days after the last dose of IMLYGIC.
- ^q Record the following information on survival status: date of contact, status (eg, alive or deceased), and date and cause of death (if applicable).

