10.1.3 Other Safety Findings

Other Safety Findings (regardless of association with an adverse event) include:

- Medication errors, overdose/underdose, whether accidental or intentional, misuse, addiction, or abuse, involving an Amgen product,
- Use of an Amgen product while pregnant and/or breast feeding,
- Transmission of infectious agents,
- Reports of uses outside the terms for authorized use of the product including off-label use,
- Accidental or Occupational exposure,

Protocol Number: 20130193
Date: 12 October 2022
Page 36 of 62

Any lack or loss of intended effect of the product(s)

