10.2 Safety Collection, Recording and Submission to Amgen Requirements

The Investigator is responsible for ensuring that safety events (adverse events, serious adverse events, product complaints, and other safety findings) observed by the Investigator or reported by the patient that occur after signing of the ICF through 30 days after the last dose of IMLYGIC; in addition, safety events (adverse events and serious adverse events) related to IMLYGIC treatment (as deemed by the Investigator) occurring 30 days after the last dose of IMLYGIC through 5 years of follow-up are recorded in the patient's appropriate study documentation. Those safety events which are considered serious must be submitted as individual case safety reports to Amgen via the applicable Amgen Safety Reporting Form (paper or electronic form) within 1 business day of Investigator's awareness. Non-serious Adverse Events must be reported in an expeditious manner, not to exceed 15 calendar days of awareness.

Protocol Exempted Events

One of the objectives of the study is to monitor for long-term safety of IMLYGIC. Hence, adverse events and serious adverse events occurring 30 days after the last dose of IMLYGIC through 5 years after the first IMLYGIC dose and deemed related to IMLYGIC by the Investigator are monitored and reported during the long term follow-up as outlined in Section 10.1. Adverse events and serious adverse events not deemed related to IMLYGIC by the investigator, and products complaints as defined in Section 10.1.4, and other safety findings as defined in Section 10.1.3 such as medication errors, overdose/underdose, misuse, addiction, abuse, off-label use involving IMLYGIC are not monitored during the long term follow-up because IMLYGIC is not administered to patients enrolled during the long-term follow-up phase of the study. Therefore, these other safety events are only monitored and reported during treatment with IMLYGIC and up to the safety visit (ie, up to 30 days after the last dose of IMLYGIC). The pregnancy

Protocol Number: 20130193 Date: 12 October 2022

and lactation cases are monitored during treatment and through 3 months after the last dose of IMLYGIC.

If any of the exempted reportable events during the long-term follow-up have a fatal outcome, they should be considered a serious adverse event and must be collected and reported individually within 1 business day from when the Investigator first becomes aware of the event.

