10.2.1 Collection of Pregnancy and Lactation Information Female Subjects Who Become Pregnant

Investigator will collect pregnancy information on any female subject who becomes pregnant following exposure to talimogene laherparepvec through 3 months after discontinuing talimogene laherparepvec.

Information will be recorded on the Pregnancy Notification Form (see Appendix D). The worksheet must be submitted to Amgen Safety within 1 business day of when investigator first becomes aware of the subject's pregnancy (Note: investigator is not required to provide any information on the Pregnancy Notification Form that violates the country or regions local privacy laws).

After receipt of the Pregnancy Notification Form, Amgen Safety will provide Investigator with a consent form and questionnaire to collect additional information. After obtaining the female subject's signed consent for release of pregnancy and infant health information, the investigator will collect pregnancy and infant health information and complete the pregnancy questionnaire for any female subject who becomes pregnant following exposure to talimogene laherparepvec through 3 months after discontinuing of the talimogene laherparepvec. This information will be forwarded to Amgen Safety. Generally, infant follow-up will be conducted up to 12 months after the birth of the child (if applicable).

Any termination of pregnancy will be reported to Amgen Safety, regardless of fetal status (presence or absence of anomalies) or indication for procedure.

While pregnancy itself is considered another safety finding, any pregnancy complication or report of a congenital anomaly or developmental delay, fetal death, or suspected adverse reactions in the neonate will be reported as an adverse event or serious adverse event. Note that an elective termination with no information on a fetal congenital malformation or maternal complication is generally not considered an adverse event, but still must be reported to Amgen as a pregnancy exposure case.

If the outcome of the pregnancy meets a criterion for immediate classification as a serious adverse event (eg, female subject experiences a spontaneous abortion, stillbirth, or neonatal death or there is a fetal or neonatal congenital anomaly) the Investigator will report the event as a serious adverse event.

Page 38 of 62

Male Subjects with Partners who Become Pregnant [or Were Pregnant at the Time of Enrollment]

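### Table 1 ends collection of pregnancy and breastfeeding exposure at 30 days after the last dose, but Sections 10.2 and 10.2.1 require 3 months, so sites working from the schedule could miss reportable cases

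*Protocol*

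**What the plan says.** The protocol gives a collection window for pregnancy and breastfeeding in four places.

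- **Table 1, footnote p.** It gives examples of other safety findings and sets one window for them all. They include "exposure to IMLYGIC during pregnancy and breastfeeding, accidental exposure, that occur after the patient has signed the ICF through 30 days after the last dose".
- **Table 1, the row that carries footnote p**, "Review of other safety findings". It is marked at baseline and during treatment. The column for the 3-monthly assessments after discontinuation is empty.
- **Section 10.2.** The opening sentence sets a single window for every kind of safety event that the investigator must record, other safety findings included: "and other safety findings) observed by the Investigator or reported by the patient that occur after signing of the ICF through 30 days after the" (it then names the final administration of IMLYGIC as the point from which the days are counted). Later, under the protocol-exempted events, the section says that pregnancy "and lactation cases are monitored during treatment and through 3 months after the last dose of IMLYGIC".
- **Section 10.2.1.** "Investigator will collect pregnancy information on any female subject who becomes pregnant following exposure to talimogene laherparepvec through 3 months after discontinuing talimogene laherparepvec". The same 3 months apply to children fathered by male subjects and to breastfeeding. Each case goes to the sponsor within 1 business day of the investigator's awareness, on a form shown in Appendix D.

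Two statements settle how such cases are classed. Section 10.1.3 lists "Use of an Amgen product while pregnant and/or breast feeding" among other safety findings, and Section 10.2.1 adds: "While pregnancy itself is considered another safety finding".

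**The concern.** Table 1 is the schedule to which Section 8.2.5 sends the reader for the content of each assessment. On pregnancy and breastfeeding it gives an earlier end than the safety section. A site can complete every marked cell of Table 1 and not raise either subject after day 30, although the safety section wants both followed for 3 months.

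At stake is the capture of individual pregnancy and lactation reports after treatment with a product derived from a live virus, in a study whose title includes long-term safety. The reporting clock starts when the investigator becomes aware of a case. If nobody asks and the patient does not volunteer it, the clock may never start.

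**Working it through.** The protocol states no figure to reproduce. The check sets the windows side by side and then does simple calendar arithmetic.

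**1. Do the texts concern the same item?** Footnote p speaks of exposure during pregnancy and breastfeeding. Section 10.2.1 speaks of a subject "who becomes pregnant following exposure to talimogene laherparepvec through 3 months after discontinuing talimogene laherparepvec". Section 10.1.3 puts use while pregnant or breastfeeding among other safety findings, and Section 10.2.1 puts pregnancy itself there. That is the class that footnote p and its row govern, so the texts largely cover the same item.

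**2. Windows as written**

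| Place | End of window |
|---|---|
| Table 1, footnote p | 30 days after last dose |
| Table 1, other-safety-findings row | no mark after discontinuation |
| Section 10.2, opening sentence | 30 days after last dose, no exception named |
| Section 10.2, later sentence | 3 months after last dose |
| Section 10.2.1 (female subjects, male subjects, lactation) | 3 months after discontinuation |

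**3. Does another row of Table 1 fill the gap?** After discontinuation the marked rows are herpetic signs and symptoms, other anticancer treatment, antiherpetic therapy, IMLYGIC-related adverse events and survival; test results may come at any time. None prompts for pregnancy or breastfeeding. The adverse-event row does not stand in for them, because Section 10.2.1 treats pregnancy as an other safety finding and only its complications or infant outcomes as adverse events.

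**4. Size of the mismatch.** Assume that 3 months is about 91 days and that discontinuation means the last dose.

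- Days inside the 3-month window and outside the 30-day window: 91 − 30 = 61.
- Share of the 3-month window: 61 / 91 = 0.67, about two thirds.

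This is a share of calendar time, not of cases.

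**5. Would one question at the first follow-up contact be enough?** Table 1, footnote c, sets contacts every 3 months ± 30 days.

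- First contact: 91 − 30 = day 61 at the earliest, 91 + 30 = day 121 at the latest.
- If it falls on day 61, then 91 − 61 = 30 days of the 3-month window are still to come.
- Second contact, counted from the last dose: 182 − 30 = day 152 at the earliest, which is after day 91.

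A prompt at the first contact alone can leave about a month uncovered. A prompt that continues until a contact at or after the end of the window does not.

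**The case against.** The strongest reply is that the safety section already works as a general rule with a specific exception. The exempted-events text of Section 10.2 limits other safety findings to 30 days and then states 3 months for pregnancy and lactation. Section 10.2.1 sets that out in detail, with its own forms and deadline. Footnote p is only a list of examples that repeats the general rule. Investigators sign up to all provisions of the protocol, and Section 8.8 provides for protocol-specific training and a completion guide. Much of this stands: the 3-month duty exists in full, and what Table 1 lacks is the prompt. It does not remove the conflict, because footnote p does more than leave the exception out. It names pregnancy and breastfeeding inside the 30-day limit.

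A second reply is that footnote p is about dosing during pregnancy, whereas Section 10.2.1 is about conception after exposure. For conception after the last dose this has some force. But on that reading Table 1 has no entry at all for those cases, and the practical result is the same.

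A reader might go further and infer that sites would miss reportable exposures. The document does not support that. Nothing in it says that sites work from Table 1 alone, and a site that applies Section 10.2.1 and the Appendix D forms could still capture every case.

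**Conclusion.** The inconsistency is real and stands in current text. Table 1 footnote p, its row and the opening sentence of Section 10.2 point to 30 days; the later sentence of Section 10.2 and all of Section 10.2.1 point to 3 months. The difference is about 61 days on the assumptions stated above. Sites that work from the schedule could miss reportable pregnancy or lactation cases between day 31 and month 3. How many depends on practice at the sites, which the document does not describe; few cases are expected, but each is reportable on its own.

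The point is limited to safety data collection. Pregnancy and lactation are not among the primary or secondary endpoints, so the incidence rates and the study size are untouched. A reader might also infer that the plan imposes no duty after day 30. That is wrong, since Section 10.2.1 does. Which window is right is for the sponsor to say. The passages must be reconciled.

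**What to change.** Reconcile footnote p, the other-safety-findings row of Table 1 and the opening sentence of Section 10.2 with the rest of Section 10.2 and with Section 10.2.1, so that one window for pregnancy and lactation appears throughout. Changing the footnote alone would leave the 30-day opening sentence of Section 10.2 in place.

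If the sponsor confirms the 3-month window:

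- take pregnancy and breastfeeding out of the 30-day clauses in footnote p and in the opening sentence of Section 10.2, with a pointer to Section 10.2.1;
- add a post-discontinuation entry to Table 1 for pregnancy and lactation that runs until a planned contact at or after the end of the window, not only at the first contact.

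The cost is a footnote, a table entry and one sentence of text, plus one extra question at contacts that are already planned.

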2. LIST OF ABBREVIATIONS

Abbreviation	Definition	
CTCAE	Common Terminology Criteria for Adverse Events	
eCRF	electronic case report form	
ECOG	Eastern Cooperative Oncology Group	
EDC	electronic data capture	
GM-CSF	human granulocyte macrophage colony-stimulating factor	
HCP	health care provider	
HSV-1	herpes simplex virus type 1	
ICF	informed consent form	
ICP	infected cell protein	
IEC	Independent Ethics Committee	
IRB	Institutional Review Board	
MedDRA	Medical Dictionary for Regulatory Activities	
PFU	plaque-forming unit	
qPCR	quantitative polymerase chain reaction	
SmPC	Summary of Product Characteristics	
USPI	United States Prescribing Information	

Page 11 of 62

Protocol Number: 20130193
Date: 12 October 2022
Page 12 of 62

